COVER PAGE

NCT #: 01109992

VERSION DATE OF THE DOCUMENT: September 12, 2016

INTEGRATED DUAL EXERCISE AND LEXISCAN PET: IDEAL PET

Version Date: September 12, 2016

Study Type: Single Center Study

Sponsor: Investigator initiated study, PI, [name]

Study Enrollment Period: June 2010 to June 2017

Principal Investigator: [name]

TABLE OF CONTENTS

Topic	Page Number
I. ABBREVIATIONS	3
II. SYNOPSIS	4-7
III. BACKGROUND	8-9
IV. SPECIFIC AIMS	10
V. SIGNIFICANCE	10-11
VI. PRIOR STUDIES	11-14
VII. SUBJECT METHODS AND SELECTION	15-16
VIII. SUBJECT ENROLLMENT	17
IX. STUDY PROCEDURES	18-21
X. BIOSTATISTICAL ANALYSIS	22-23
XI. RISKS AND DISCOMFORT	23-24
XII. POTENTIAL BENEFITS	25
XIII. MONITORING AND QUALITY ASSURANCE	25-26
XIV. REREFENCES	27

ABBREVIATIONS USED:

Myocardial Blood Flow: MBF

Positron Emission Tomography: PET

Computed Tomography: CT

Myocardial perfusion imaging: MPI

Coronary Flow reserve: CFR

Coronary artery disease: CAD

Lexiscan + Exercise: Lexercise

SYNOPSIS

Title of Study: Integrated Dual Exercise And Lexiscan PET: IDEAL PET

Planned Study Period: From 4Q2010 - 2Q2017

Study Objective(s)

Aim 1: To *assess the tolerability and safety* of combined symptom limited exercise stress test with Lexiscan (Lexercise PET) compared to Lexiscan alone (Lexiscan PET).

Aim 2: To *assess the image quality* of Lexercise compared to Lexiscan PET.

Aim 3: To compare *relative and absolute myocardial perfusion imaging* with Lexercise compared to Lexiscan PET to identify CAD.

Planned Total Number of Study Centers and Location

Single study center, Brigham and Women's Hospital, Boston, MA, United States

Design and Methodology

This is a single-center, prospective cohort study of subjects undergoing clinically indicated PET/CT MPI, with documented coronary artery disease or an intermediate to high pretest likelihood of coronary artery disease. Following the clinical study, the research study is explained to the subjects. Consenting subjects will return on another day (next calendar day or later) for a repeat stress study with Lexercise or a repeat Lexiscan stress PET. Approximately 50 subjects (not more than 16 patients with normal Rubidium-82 or N-13 ammonia PETMPI, 10 healthy volunteers and 24 patients with reversible perfusion defects) will be enrolled in this study. After successful screening and enrollment, 13 random subjects (8 normal and 5 ischemic) will return for repeat Lexiscan PET, and 37 subjects will return for a Lexercise PET/CT MPI. Lexiscan PET will be performed per standard protocol. For Lexercise, a symptom limited exercise treadmill study with Lexiscan injection at peak exercise is performed. Rubidium-82 or N-13 ammonia will be injected and PET/CT images will be obtained in a list mode acquisition. Images will then be unlisted and myocardial blood flow computed.

Number of Subjects Planned

Approximately 50 subjects will be enrolled into the study.

Main Selection Criteria

Subjects will be eligible if they meet all of the following inclusion criteria and none of the exclusion criteria:

Inclusion criteria:

- Age > 18 years
- Clinically indicated Rubidium-82 or N-13 ammonia PET study
- Ten healthy volunteers recruited using web based advertisements.
- Known coronary artery disease (prior percutaneous coronary intervention, prior coronary artery bypass surgery or Q wave MI on ECG) or intermediate to high pretest likelihood of CAD
- Able to exercise on a treadmill
- Able and willing to provide informed consent to participate in the study

Exclusion criteria:

- Contraindications to exercise stress testing such as
 - unstable angina
 - known severe left main coronary artery stenosis
 - severe or uncontrolled heart failure
 - uncontrolled atrial or ventricular arrhythmias
 - symptomatic hypotension or severe hypertension (systolic blood pressure < 90 or > 200 mmHg, respectively)
 - > 1st degree atrioventricular block in the absence of a functioning pacemaker.
- Contraindications to Lexiscan use such
 - Allergy or intolerance to aminophylline or regadenoson
 - Known severe or oxygen dependent bronchoconstrictive or bronchospastic lung disease [e.g., asthma, wheezing, chronic obstructive pulmonary disease (COPD), etc.].
 - Sick sinus syndrome
 - History of heart transplantation.
 - Dialysis
 - Subject requires emergent cardiac medical intervention or catheterization after the clinical study.
 - Documented myocardial infarction (MI) ≤ 30 days prior to enrollment.
 - History of percutaneous coronary intervention (PCI) ≤ 4 weeks prior to enrollment.

- History of coronary artery bypass graft (CABG) \leq 8 weeks prior to enrollment.
- Severe LV dysfunction, with ejection fraction of $< 30\%$
- Serious non-cardiac medical illness (e.g., disseminated malignancy, severe neurological dysfunction at time of baseline PET study) or a social situation which will preclude research study participation
- History of seizure disorder

Discontinuation criteria:

Subjects should be discontinued for the following discontinuation criteria

- Subject does not fulfill inclusion or exclusion criteria
- Subject experiences a serious or intolerable adverse event
- In the Investigator's opinion, the subject is non-compliant with the protocol requirements (protocol violation)
- Subject's health would be jeopardized by continued participation
- Subject wishes to withdraw consent

Lexiscan will not be administered to patients with clinical or EKG evidence on ischemia during exercise treadmill testing. Clinical or EKG abnormalities during treadmill testing that would preclude administration of Lexiscan are listed below:

- a) Clinical
 - a. Severe chest pain
 - b. Severe lightheadedness or dizziness,
 - c. Severe shortness of breath
 - d. Exercise induced hypotension ($> 10\text{mm Hg}$ decrease in systolic blood pressure)
 - e. Exercise induced hypertension (systolic blood pressure $> 210\text{ mm Hg}$)
- b) ECG changes
 - a. Significant ST segment depression ($\geq 2\text{ mm}$)
 - b. Significant ST segment elevation ($\geq 1\text{ mm}$)
 - c. Sustained ventricular or atrial tachycardia,
 - d. Exercise induced heart block

Statistical Plan:

The overall aim of this pilot study of 50 patients is to assess the tolerability, safety, diagnostic accuracy and image quality between Lexiscan with symptom limited exercise compared to Lexiscan alone.

Aim 1. For this aim, we will compare the reported side effect profile for Lexercise to Lexiscan PET, using a Pearson Chi square test. A P-value of <0.05 will be considered significant.

Aim 2: For this aim, we will compare objective measures of image quality including signal to noise ratio using dynamic Rubidium-82 or N-13 ammonia images, the frequency of misregistration between PET and CT, the frequency of presumed motion artifact and bowel radiotracer activity. These measures will be compared using a student's t-test or a Pearson Chi square test, as appropriate. A P-value of <0.05 will be considered significant.

Aim 3: For this aim, we seek to compare measures of semi quantitative relative perfusion, absolute perfusion and LVEF using the Lexiscan alone compared to Lexercise PET. Firstly, we will compare semi-quantitative defect size, severity and reversibility between the Lexercise and Lexiscan PET studies. Based on the results of one prior study using N-13 ammonia and comparing dipyridamole versus treadmill exercise², a sample size of 24 subjects with reversible defects should be adequate to identify if significant differences exist between Lexercise and Lexiscan PET protocols. Next, we will compare the differences in regional rest and peak stress myocardial blood flow and coronary flow reserve in the defect territory compared to normal territory between the Lexercise and Lexiscan protocols. Finally, we will study the changes in LVEF from rest to peak stress in Lexercise versus Lexiscan PET studies in the normal and ischemic subjects.

[figure not shown]
I. BACKGROUND:

Myocardial perfusion imaging (MPI) with positron emission tomography (PET) is more accurate than single photon emission computed tomography (SPECT)³, enables non-invasive quantitation of absolute myocardial blood flow (MBF), and is particularly helpful in the obese individuals and those that are unable to exercise.³ Presently PETMPI is indicated only for subjects that are unable to exercise⁴,

primarily because exercise stress is not easy with PET. However, due to superior image characteristics, faster pace, and radiation dosimetry (compared to Thallium-201), exercise PET with Rubidium-82 is being viewed as an excellent alternative to exercise SPECT. This has become more important lately with the recent shortage of Technetium labeled radiotracers. Although exercise PET is feasible with Rubidium-82,² the workflow is challenging due to its short-half-life (75 seconds). Exercise PET with N-13 ammonia has been studied, but this is only possible in sites with an onsite cyclotron and the production and delivery of N-13 ammonia have to be coordinated with the PET scanner due to its 10 minute half-life.² Finally, in high volume nuclear cardiology laboratories, routine clinical use of exercise PET poses the concern of high radiation exposure to staff.⁵ This is primarily related to the fact that, after the PET radiotracer is injected on the treadmill, the staff is directly and closely exposed to the radioactive patient (while walking and positioning the subject to the scanner immediately after radiotracer injection).

Effects of exercise and vasodilator stress on myocardial blood flow:

Exercise is the most important physiological stimulus that increases myocardial oxygen demand. Exercise results in vasodilation of the normal epicardial coronary arteries (Figure, Top panel).⁶ The resultant increase in coronary blood flow and shear stress lead to endothelial release of nitric oxide and several other vasoactive mediators that cause further vasodilation of the downstream microvasculature and increased MBF. In contrast, diseased epicardial coronary arteries vasoconstrict in response to exercise resulting (Figure, bottom panel) in an increased flow gradient with reduced blood flow to the downstream microvasculature during exercise as compared to normal territories.

Wilson R. N Engl J Med 1996;334:1735-1737

Vasodilator stress agents do not typically result in vasoconstriction of diseased coronary arteries. They produce differential vasodilation of both normal and diseased coronary arteries by predominantly by an endothelium independent mechanism resulting in estimation of primarily endothelium independent changes in MBF, and to a lesser extent endothelium independent changes in MBF.⁷

Combined standard symptom limited exercise stress testing with injection of Lexiscan at peak exercise (Lexercise PET) may be a novel protocol to optimally image maximal endothelium dependent (exercise) and endothelium independent (Lexiscan) alterations in MBF, using relative and absolute myocardial perfusion PET. Symptom limited exercise produces endothelial activation and vasodilation of normal and vasoconstriction of diseased coronary arteries. Addition of vasodilator stress at maximal exercise results in further (maximal) vasodilation of the normal coronary arteries; but minimal or no additional

vasodilation of the vasoconstricted diseased coronary arteries. This may result in improved defect contrast compared to the normal coronary arteries and better detection of CAD. Indeed a prior study demonstrated that defect size is larger with treadmill exercise stress compared to vasodilator stress with dipyridamole.⁸ Also, the precise reasons for larger perfusion defects with exercise compared to dipyridamole PET were not studied; although, true ischemia from exercise was proposed as a possible mechanistic link for larger perfusion defects with exercise. If endothelial dysfunction and true vasoconstriction are imaged with exercise PET, then, we can expect to metabolic abnormalities (switch from fatty acid to glucose metabolism) in the corresponding myocardial segments that may be imaged using tracers of fatty acid metabolism such as β Methyl-*p*-[123I]-iodophenyl-pentadecanoic acid (BMIPP) or C-11 Palmitate. Lastly, quantitative MBF is estimated predominantly with vasodilator stress and occasionally with bicycle exercise stress.⁹ Quantitative PET with Lexercise PET may be a novel method to image combined alterations in MBF related to both endothelium dependent and independent mechanisms of MBF.

II. SPECIFIC AIMS:

The overall purpose of the proposed research study is to examine in detail, using relative and quantitative Rubidium-82 or N-13 ammonia PET, the feasibility, safety, utility and the mechanistic basis of combined symptom limited exercise treadmill test with vasodilator stress compared to vasodilator stress alone in the evaluation of known or suspected coronary artery disease. The following specific aims are proposed:

Aim 1: To **assess the tolerability and safety** of the combined symptom limited exercise and Lexiscan protocol (Lexercise PET) compared to Lexiscan alone (Lexiscan PET).

Hypothesis 1: Lexiscan will cause further/maximal vasodilation in a subject that is already vasodilated from exercise; therefore, the safety of this protocol needs to be ascertained. Lexiscan is expected to be well tolerated when injected during maximal exercise stress without any increase in major adverse events.

Aim 2: To **assess the image quality** of Lexercise PET compared to Lexiscan.

Hypothesis 2: Image quality as assessed by myocardial count density and heart to liver ratio will be superior with Lexercise compared to Lexiscan. However, misregistration artifacts from upward diaphragmatic creep will be higher with Lexercise compared to Lexiscan.

Aim 3: To compare **relative and absolute PET** with Lexercise compared to Lexiscan PET in identifying CAD.

Hypothesis 3: Lexercise PET offers the advantage of imaging reduced myocardial blood flow from vasoconstriction in diseased territories and maximal vasodilation in normal territories. Therefore, in patients with ischemic scans, the defect contrast on relative will be better with Lexercise compared to Lexiscan PET. We hypothesize that the differences in regional CFR between normal and abnormal territories will be greater with Lexercise compared to Lexiscan.

Significance of the mechanistic questions of this proposal:

The overall goal of this proposal is to evaluate the feasibility, utility and mechanistic underpinnings of a novel protocol incorporating combined maximal symptom limited exercise treadmill test with Lexiscan compared to Lexiscan alone. The combined standard symptom limited exercise stress testing with Lexiscan has several novel clinical and research applications:

1. This protocol provides exercise data (hemodynamic, electrocardiographic and clinical data) combined with high quality PET imaging that is important in patient management.
2. A PET MPI study can be performed with physiological exercise stress using any of the available flow tracers (Rubidium-82, N-13 ammonia, or the new compound BMS747158, an F-18 labeled agent) with minimal radiation exposure to the staff.
3. This protocol makes it feasible to assess both endothelium dependent (exercise) and endothelium independent (Lexiscan) mechanisms affecting MBF.
4. This combined assessment may prove to have a superior diagnostic accuracy compared to Lexiscan alone in diagnosing milder degrees of stenoses and balanced ischemia due to ECG changes, symptoms, hemodynamic changes, and improved defect contrast on relative and absolute PET.⁸
5. Also, using Rubidium-82 or N-13 ammonia and exercise PET, peak stress left ventricular ejection fraction can be computed.
6. Finally, the results of this study could be extrapolated to stress imaging with cardiac magnetic resonance imaging, making exercise CMR feasible.

b) Previous studies leading up to or supporting the proposed research

A major strength of this project is that it represents an outgrowth of techniques pioneered at BWH. Within our existing Division of Nuclear Medicine/PET and Cardiovascular Imaging, this project is a natural extension of our work to date. We have extensive clinical and research experience with Rubidium-82 and N-13 ammonia PET, and have performed over 6000 clinical studies since the initiation of our PET program in the fall of 2003. We have been using Lexiscan with Rubidium-82 PET since January 2009 and with N-13 ammonia PET since July 2011. Also, quantitative myocardial blood flow estimates have been routinely performed using a home grown software program (soon to be commercially available).

Rationale for specific aim 1:

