	Exercise Stress	Dipyridamole Stress	p Value	Correlation	Significance of Correlation
Summed stress score	9.1 ± 5.7	6.9 ± 5.9	<0.01	0.80	<0.001
Summed rest score	3.4 ± 3.3	3.2 ± 2.8	NS	0.79	<0.001
Summed difference score	5.8 ± 4.7	3.7 ± 4.6	<0.02	0.61	0.001
LV defect size (stress) (%)	19.3 ± 11.5	13.8 ± 13.6	<0.02	0.62	0.001
LV defect size (rest) (%)	8.1 ± 9.4	6.4 ± 6.5	NS	0.57	0.003

Values are mean ± SD.

LV = left ventricle; PET = positron emission tomography.

Myocardial count density of N-13 ammonia was significantly greater with dipyridamole compared to exercise stress. Successful performance of exercise ammonia required coordination between the cyclotron team and the imaging team. The authors concluded that treadmill exercise produces larger and more severe perfusion defects than dipyridamole and may reflect true ischemia.

III. STUDY METHODS

This is a single-center, prospective cohort study of subjects undergoing clinically indicated PET/CT MPI, with documented coronary artery disease or an intermediate to high pretest likelihood of coronary artery disease based on age gender and symptoms as described in the ACC/AHA/ASNC appropriate use criteria for cardiac radionuclide imaging.¹² Following completion of the clinical study, the research study is explained to the subjects. Consenting subjects will return on another day for a repeat stress study with Lexercise or a repeat Lexiscan stress PET. Approximately 50 subjects (not more than 16 patients with normal Rubidium-82 PETMPI and 34 with reversible perfusion defects) will be enrolled in this study. After successful screening and enrollment, 13 random subjects (8 normal and 5 ischemic) will return for repeat Lexiscan PET, and 34 subjects will return for a Lexercise PET/CT MPI, on the next calendar day or within 2 weeks of the clinical Rubidium-82 or N-13 ammonia PET study.

SUBJECT SELECTION

Main Selection Criteria

Subjects will be eligible if they meet all of the following inclusion criteria and none of the exclusion criteria:

Inclusion criteria:

- Age > 18 years
- Clinically indicated Rubidium-82 or N-13 ammonia PET study
- Ten healthy volunteers recruited using web based advertisements.

- Known coronary artery disease (prior percutaneous coronary intervention, prior coronary artery bypass surgery or Q wave MI on ECG) or intermediate to high pretest likelihood of CAD
- Able to exercise on a treadmill
- Able and willing to provide informed consent to participate in the study

Exclusion criteria:

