- Hospital in-patients with request for pharmacologic stress: Attending physicians will be asked if they felt comfortable introducing the study to their subjects that they schedule for in-patient pharmacologic stress myocardial perfusion study verbally during their visit. If the physician introduces the study verbally, the subject will be asked if they would like to speak with a coordinator after the visit. If they would like to speak with someone, the coordinator will be notified and they will explain the study to the subject and go over the inclusion and exclusion criteria for the study. If they are interested in participating in the study an appointment will be made for their first visit.
- Special attention will be paid to enroll women and minorities in the study.
- Ten healthy volunteers will be recruited for this study using web based advertisements. They will all undergo Lexiscan (regadenoson) followed by Lexercise protocol (exercise + regadenoson) on a separate day.

b) Procedures for obtaining informed consent (including timing of the consent process)

For subjects interested in speaking to a study staff, Study PI, will go over the inclusion and exclusion criteria and will describe the study and procedures to the potential subject over the phone or in person. If the subject qualifies and is interested he/she is encouraged to discuss the study with his/her primary care physician or family members. Upon arrival for the study, the subject will be given a copy of the consent form to read. After the subject has finished reading the consent form, one of the physician investigators will describe the study in detail and answer any questions or concerns

the subject might have. If the subject agrees to participate in the study they will be asked to provide his/her written informed consent. Subjects will be given a copy of the signed consent form for their records. The investigator will inform the subject that they have the alternative not to participate in the study and can withdraw their consent at any point during the study.

The subjects will be given as much as 2 weeks to consider participation in the trial. Pregnant women and minors are excluded from this trial. Subjects that are determined by the physician to be unable to consent due to their physical or mental condition will not be enrolled in this trial.

V. STUDY PROCEDURES

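### Aim 1 sets no breakdown by cohort: at most 19 of 37 Lexercise exposures are in ischemic patients and 10 are in healthy volunteers, so a pooled safety result would look firmer than the patient data allow

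*Combined protocol and SAP*

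**What the plan says.** The Synopsis (Design and Methodology) enrolls "not more than 16 patients with normal Rubidium-82 or N-13 ammonia PETMPI, 10 healthy volunteers and 24 patients with reversible perfusion defects" and then divides the second scans: "13 random subjects (8 normal and 5 ischemic) will return for repeat Lexiscan PET, and 37 subjects will return for a Lexercise PET/CT MPI". Section IV (Subject Enrollment) says of the volunteers: "They will all undergo Lexiscan (regadenoson) followed by Lexercise protocol (exercise + regadenoson) on a separate day". No volunteer can therefore be in the repeat-Lexiscan group.

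Section III (Study Methods) gives another mix, "not more than 16 patients with normal Rubidium-82 PETMPI and 34 with reversible perfusion defects", and another Lexercise count, "34 subjects will return for a Lexercise PET/CT MPI". Its selection criteria still list ten volunteers.

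For Aim 1, the Statistical Plan and Section VI (Biostatistical Analysis) say "we will compare the reported side effect profile for Lexercise to Lexiscan PET, using a Pearson Chi square test", and add "A P-value of <0.05 will be considered significant". Neither place states a stratum, a pairing or which Lexiscan scans are the comparator, and both call the 50 subjects patients. Aim 2 is equally silent: "These measures will be compared using a student's t-test or a Pearson Chi square test, as appropriate". Aim 3 does distinguish normal from ischemic subjects for the change in LVEF.

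Section II (Specific Aims) places the purpose of the study in the evaluation of known or suspected coronary disease.

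**The concern.** A statement that Lexercise is well tolerated will be read as applying to the patients for whom the protocol is proposed. If it rests on one total, more than a quarter of the exposures come from volunteers outside that population, and only about half come from patients with a reversible defect. A problem specific to ischemic patients would be diluted, and an absence of events would look more reassuring than the ischemic data support.

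There is also a question about the comparison itself. The fraction sent to repeat Lexiscan differs by cohort, so the answer could depend on which Lexiscan scans are set against Lexercise, and the plan does not say which.

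**Working it through.** **Counts (Synopsis, with Section IV).** The stated totals reproduce: 16 + 10 + 24 = 50 and 13 + 37 = 50. By subtraction:

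| Cohort | Enrolled | Repeat Lexiscan | Lexercise |
|---|---|---|---|
| Ischemic | 24 | 5 (21% of cohort) | 19 |
| Normal scan | 16 | 8 (50%) | 8 |
| Volunteers | 10 | 0 | 10 |
| Total | 50 | 13 | 37 |

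Ischemic patients are 19/37 = 51.4% of the Lexercise group and 5/13 = 38.5% of the repeat-Lexiscan group. Volunteers are 10/37 = 27.0% and 0.

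Nineteen is a maximum, because the discontinuation criteria withhold Lexiscan when listed clinical or ECG abnormalities appear on the treadmill.

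**Dilution.** An excess confined to ischemic patients is multiplied by 19/37 on pooling: 20 × 19/37 = 10.3 points. Pairing does not change this factor.

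**Zero events.** The exact one-sided 95% upper limit is 1 − 0.05^(1/n):

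- all 37 Lexercise subjects: 7.8%
- the 27 patients (19 + 8): 10.5%
- the 19 ischemic patients: 14.6%

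The upper ends of two-sided 95% intervals are 9.5%, 12.8% and 17.6%. An event with a true 5% rate in ischemic patients would be seen at least once in 19 with probability 1 − 0.95^19 = 62%.

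**Sensitivity to the Study Methods counts.** There 16 + 34 = 50, but 13 + 34 = 47. Taking 34 ischemic and 16 normal-scan patients less the 13 gives 29 + 8 = 37 Lexercise subjects, not the 34 printed. On that basis 20 points becomes 20 × 29/37 = 15.7, and the zero-event limit in 29 is 1 − 0.05^(1/29) = 9.8%. The fractions sent to repeat Lexiscan would still differ: 8/16 = 50% against 5/34 = 15%.

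**Confounding if 37 are compared with 13.** The documents give no side-effect rates by cohort, so the rates here are assumptions, with no true protocol effect.

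At 30/10/5% (ischemic/normal/volunteer):

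- Everyone: (19 × 0.30 + 8 × 0.10 + 10 × 0.05)/37 = 18.9%, against (5 × 0.30 + 8 × 0.10)/13 = 17.7%; a gap of 1.2 points.
- Volunteers dropped, no stratification: (5.7 + 0.8)/27 = 24.1% against 17.7%; a gap of 6.4 points.

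Other assumed rates, everyone included. The false-positive rate is by exact enumeration of the uncorrected chi-square, two-sided 0.05 (sidedness is not stated in the plan):

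| Assumed rates | Gap, points | False-positive rate |
|---|---|---|
| 40/20/10% | −0.1 | 4.3% |
| 40/10/10% | +3.9 | 3.8% |
| 30/30/10% | −5.4 | 7.3% |
| 20/20/50% | +8.1 | 7.0% |
| 50/50/5% (extreme) | −12.2 | 11.7% |
| 60/10/60% (extreme) | +20.0 | 17.7% |

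If all Lexiscan scans are the comparator (50 first plus 13 repeat), 29/63 = 46% are ischemic and 10/63 = 16% are volunteers, so the mix still differs from 51% and 27%.

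**Within-subject comparison.** If each of the 37 is compared with their own Lexiscan scan, the mix is 19/8/10 on both sides and cannot confound.

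**Power of a stratified test.** For a 20-point excess over a base of 12 to 28%, 19 against 5 has about 9 to 11% power (rough normal approximation).

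**The case against.** The strongest reply is that the plan never says it compares the 37 with the 13. It compares Lexercise with Lexiscan. Section V (Study Procedures) analyzes the Lexiscan images from the clinical study beside the Lexercise images, and every volunteer has both protocols. Each Lexercise subject thus has an own control. This stands: a reader might infer that Aim 1 is confounded by design, but the documents do not support that. Even with the 13 as comparator, the imbalances can nearly cancel, and their direction is not fixed.

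Three further points have force. Pooling is inferred from silence, and nothing bars a report by cohort. The documents do not say that ischemic patients carry the greatest risk from Lexercise, and normal-scan patients also belong to the known-or-suspected disease population. A reader might also extend the point to Aim 2, but nothing in the documents gives a size for an effect of cohort mix on image quality.

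The reply does not remove the main point. The named test is ordinarily one for independent samples, no pairing is stated, and pairing would not cure dilution. Troponin is a case where own controls may be missing: Section V has no blood draw at the volunteers' Lexiscan visit and describes no research draw at the patients' clinical scan. A Lexiscan troponin collected by the study may then exist only in the 13.

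**Conclusion.** The point holds for Aim 1 as a matter of reporting and of specifying the comparison. On the Synopsis counts, a pooled result halves any signal confined to ischemic patients, and the zero-event limit of 7.8% is about half the 14.6% that 19 ischemic patients support; for all 27 patients it is 10.5%. These figures assume that Aim 1 is analyzed as one total, that all 19 receive Lexiscan after exercise, and that the Synopsis counts govern. On the Study Methods counts the dilution is smaller.

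Confounding by cohort mix is conditional. It arises only if the 13 repeat scans, or all Lexiscan scans together, are the comparator. With everyone included it is then about 0 to 8 points in either direction under moderate assumed rates, and it is absent in a within-subject comparison. No claim is made about the size of any effect on Aim 2.

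**What to change.** - State the comparator. Make Lexercise against the same subject's own Lexiscan scan the main analysis, with McNemar's test for yes/no outcomes and a paired test for continuous ones. Confirm that side effects at the clinical Lexiscan scan are recorded in a form that can be paired.
- Report Aim 1 safety separately for ischemic patients, normal-scan patients and volunteers, with exact confidence intervals. Base the safety statement on patients, show the ischemic estimate beside it, and do not rest it on a total that includes volunteers.
- In any comparison with the 13 repeat-Lexiscan subjects, leave volunteers out and stratify by normal against ischemic scan. Do both together, since dropping volunteers without stratifying can increase the bias (1.2 to 6.4 points in the example). Treat the result as descriptive.
- Reconcile the cohort and Lexercise counts in the Synopsis and Section III.

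This is a change of wording in the analysis plan and needs no new data. The price is wider intervals within cohorts.
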